Transdermal alcohol monitors can provide noninvasive, continuous monitoring of alcohol use by detecting ethanol diffused through the skin.^{27,31} Secure Continuous Remote Alcohol Monitor (SCRAM) anklet (Alcohol Monitoring Systems, Inc.) is the most widely used transdermal monitor but is designed to be used for law enforcement purposes.³² However, wider application of SCRAM anklet in clinical and intervention settings is limited by its shortcomings including its large size, high cost, and social stigma.^{20,25,29} The newest generation of wrist-worn alcohol monitor (BACtrack Skyn) is designed for consumer use and

addresses these limitations. The device looks like a fitness tracker, is inexpensive, samples up to every second, and transmits and shows data in real-time via a smartphone app. These advantages make this wrist-worn alcohol monitor a potentially ideal tool to be incorporated into smartphone-based intervention for alcohol use. However, prior to its application in research, thorough validation investigations of the monitor are needed. In this project, we will validate the Skyn monitor among 20 HIV+ drinkers and 20 HIV- drinkers (as comparison group) in both laboratory and field settings.

Fig.1. BACtrack Skyn Alcohol Monitor

5. Specific Aims:

Aim 1: Assess the validity and reliability of the Skyn monitor through comparison with laboratory grade breathalyzer in two fixed-dose lab alcohol administration sessions (Sec. 4.3, 4.5)

Hypothesis 1a: The monitor will be able to detect alcohol use at a low threshold (e.g., one drink).

Hypothesis 1b: The parameters of transdermal alcohol concentration (TAC) (e.g., peak, time-to-peak, area under the curve) will be correlated with number of drinks and breath alcohol concentration (BrAC).

Hypothesis 1c: The TAC readings in two lab sessions will show high correlation (test-retest reliability).

Aim 2: Validate Skyn monitor in daily life using a 2-week ecological momentary assessment (EMA), and evaluate its acceptability and usability for daily alcohol monitoring (Sec.4.4)

Hypothesis 2a: The monitor detected drinking episodes will correspond with self-reports in EMA.

Hypothesis 2b: The TAC readings will correlate with number of drinks in each drinking episode.

Exploratory Aim: Explore factors (e.g., gender, HIV status) that may be associated with individual differences in monitor readings (e.g., peak, time-to-peak, correlation with consumption level).

6. Research Plan:

Overview

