This study will include two parts: laboratory and field validation of the Skyn monitor (Fig. 2). We will need complete data from 20 HIV+ drinkers (~50% male) and 20 HIV- drinkers (~50% male), but we will screen to 160 participants to account for potential screen failure and drop out. Participants will be invited to complete all components of the study or only the field test portion given the COVID pandemic. The PI will decide who will complete all components and who will complete only the field testing. Participants will first complete an alcohol administration session (Lab Session 1) at the simulated bar lab, where they will consume 3 standard drinks (i.e., 3 12oz beers) at a determined consumption rate (30min). The transdermal alcohol concentration (TAC) readings collected from the Skyn monitor will be compared with breath alcohol concentration (BrAC) and may be compared with the Secure Continuous Remote Alcohol Monitor (SCRAM; Alcohol Monitoring Systems, Inc.) anklet. After completing Lab Session 1, during a two-week field test, participants will use the Skyn monitor and record drinking episodes using an EMA app. After the field test, participants will return to the bar lab to complete a second alcohol administration session using the same procedures as in Lab Session 1 to obtain test-retest reliability of the monitor. They will also complete a questionnaire on the acceptability and usability based on their experience with the Skyn monitor and its smartphone app.

Of note, BACtrack Skyn monitor has been approved in our previous study ([IRB201700455](#) for laboratory alcohol administration study where participants wear the monitor while they self-administer alcohol in the bar lab).

[figure not shown]

Figure 2. Study Procedures

Participants

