Data sources and management. In the lab sessions, we will record information about the drinking episode (start and end times of each beer) and the BrAC data (time, reading). TAC readings from Skyn monitor and SCRAM anklet will later be downloaded from their respective web porter as a csv/Excel file and stored on a secured server at UF. In the field test, EMA data is cloud-based and will be downloaded to a secured server at UF on a daily basis when active data collection is in process. All data will be linked using the 8-digit ID code assigned to the participant.

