Analysis plan for Aim 1: *Assess the validity and reliability of the Skyn monitor through comparison with laboratory grade breathalyzer in two fixed-dose lab alcohol administration sessions.* H1a. Threshold of detection. We define the threshold of detection as the consumption level with a 60% or higher detection rate. Rate of successful detection at the end of 1 beer, 2 beers, and 3 beers will be calculated respectively. This will be done by observing the data series and curves from the monitor readings.^{45,48} Successful detection of consumed alcohol is defined by a TAC peak (e.g., $\geq 0.02\text{g/dL}$) with a reasonably visible elevation slope for absorption (i.e., TAC curve goes up at a reasonable pace) and a declination slope for elimination (i.e., TAC curve goes down at the reasonable pace). H1b1. Relationship between TAC and number of drinks. The means of peak TAC readings and the areas under the curve will be calculated for 1, 2, and 3 drinks respectively. We expect a linear increase of peak TAC and area under the curve as number of drinks increase from 1 to 3. H1b2. Relationship between TAC and BrAC. We will examine the relationship between TAC and BrAC in three ways. First, a simple correlation will be calculated between recorded peak TAC and peak BrAC. A scatter plot will be produced to illustrate the bivariate correlation between these two readings. Second, the Bland-Altman method^{55,56} will be used to examine the magnitude of peak differences between TAC and BrAC. The average of paired TAC and BrAC peak values are plotted on x-axis, and the difference between them on y-axis. Stable TAC results across all BrAC levels will line up with a zero slope, which will suggest there is no systematic bias in estimating BrAC. Third, we will calculate the time-to-peak based on recorded TAC and BrAC readings. Their differences will be calculated to determine time delays in BrAC to TAC peaks. All these analyses will be conducted for TAC and BrAC readings obtained after each beer respectively. H1c: Two-week test-retest reliability. Pearson correlational coefficients will be calculated to indicate test-retest reliability using TAC peak /time-to-peak for each participant in two lab sessions. A correlation $\geq .7$ indicates good test-retest reliability.

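### The lab detection rates after beer 1 and beer 2 are cumulative readings inside a three-beer session, not the one- and two-drink rates that the 60% threshold needs

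*Combined protocol and SAP*

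**What the plan says.** The drinking procedure is in section 6 of the combined protocol and SAP. The Overview says participants come to the bar lab, where "they will consume 3 standard drinks (i.e., 3 12oz beers) at a determined consumption rate (30min"). Lab Session 1 makes clear that the 30 minutes apply to each beer, 15 to drink it and 15 to rest, so the beers start at 0, 30 and 60 minutes of one 90-minute period. Lab Session 2 repeats this. Breath alcohol (BrAC) is read every 30 minutes during drinking and about every 15 minutes afterwards. Under Data sources and management, "we will record information about the drinking episode (start and end times of each beer) and the BrAC data (time, reading").

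The Analysis plan for Aim 1 then works beer by beer:

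- **H1a.** "We define the threshold of detection as the consumption level with a 60% or higher detection rate", and "Rate of successful detection at the end of 1 beer, 2 beers, and 3 beers will be calculated respectively". A detection needs a TAC peak (0.02 g/dL is given as an example), a visible rise, and "a declination slope for elimination (i.e., TAC curve goes down at the reasonable pace"). This serves Hypothesis 1a in section 5: "The monitor will be able to detect alcohol use at a low threshold (e.g., one drink").
- **H1b1.** "The means of peak TAC readings and the areas under the curve will be calculated for 1, 2, and 3 drinks respectively", with a linear increase expected. It serves Hypothesis 1b, that TAC parameters "will be correlated with number of drinks and breath alcohol concentration (BrAC").
- **H1b2.** The peak correlation, Bland-Altman and time-to-peak comparisons of TAC with BrAC are repeated after each beer.

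The plan expects a delay from BrAC to TAC and means to estimate it, but gives no size. It states no time window for each beer's detection call and no limits for the AUC.

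**The concern.** The wording treats one, two and three beers as three consumption levels. The design supplies one level, three beers, looked at three times on the way up. Beer 2 begins 15 minutes after beer 1 ends, so a reading labelled one drink is really a reading at about 30 minutes, before a delayed signal has had time to peak and fall.

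This bears on the main lab claim. The 60% rule decides Hypothesis 1a, whose example is one drink, and its answer partly reflects when the curve is read. For H1b1, a quantity that can only accumulate may be taken as evidence that the device tracks dose.

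**Working it through.** **1. The plan's own figure.** There is none for the detection threshold or the dose trend. The only Aim 1 power calculation is n = 40 for 80% power at r = .60. With two-sided alpha .05 (assumed for Aim 1), Fisher's z gives Φ(atanh(.60)·√37 − 1.960) = Φ(4.216 − 1.960) = 98.8%. That mismatch is conservative and separate; nothing below depends on it.

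**2. When could a fall be seen?** There are two ways to read H1a.

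- Before the next beer: the TAC of one beer must rise, peak and fall by 30 minutes, and that of two beers by 60.
- Later: by then the next beer is in the body, and the fall is that of the three-beer curve.

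On neither reading is the fall of a one- or two-drink episode observed. A TAC rise before beer 2 does come from beer 1 alone. Leaving false-positive readings aside, detection on that rise is therefore a lower bound for one-drink detection.

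**3. Illustration.** Everything here except beer size, strength and timing is assumed.

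- Ethanol per beer: 12 oz at 4.5% ABV = 12.6 g, drunk evenly over 15 minutes.
- Concentration added per beer: 12.6 / (r × kg × 1000) × 100 g/dL. For r = 0.68 and 80 kg this is 0.023 before elimination.
- Grid: r 0.55, 0.68; weight 60, 70, 80, 90, 100 kg; absorption half-life 2, 5, 10, 15 min; elimination 0.010, 0.015, 0.020 g/dL/h. That is 2 × 5 × 4 × 3 = 120 scenarios.
- TAC: first-order lag, dTAC/dt = (gain × BAC − TAC)/lag, without noise.

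Any fall at all, however small, was counted. The first and last result columns do not depend on gain; the largest fall is at gain 1.

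| Lag (min) | Fall before next beer, beer 1 / beer 2 (of 120) | Largest fall (g/dL) | Highest TAC by 30 min as share of one-beer-alone peak, median (range) |
|---|---|---|---|
| 0 | 54 / 52 | 0.0028 | 100% (79–100) |
| 5 | 24 / 24 | 0.0006 | 95% (66–100) |
| 15 | 0 / 0 | – | 75% (45–99) |
| 30 | 0 / 0 | – | 58% (31–91) |
| 60 | 0 / 0 | – | 46% (21–82) |

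At lags of 15 minutes or more, the one-beer-alone peak comes after beer 2 has started in all 120 scenarios (33–79 min at lag 15, 39–97 at lag 30, 45–121 at lag 60). A second model, with different assumed values, put that peak at 50–113 minutes.

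**4. If the fall is judged later, so that only the 0.02 g/dL peak matters.** At gain 1, the scenarios reaching it by the end of beer 2, against two beers given alone and followed through, are:

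- lag 0: 108 against 109
- lag 5: 102 against 109
- lag 15: 86 against 101
- lag 30: 55 against 92 (46% against 77%)
- lag 60: 14 against 72

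The 60% line is 0.60 × 120 = 72. The two-beer verdict therefore changes at lags 30 and 60, at lag 60 on an exact tie. One beer alone at gain 1 reaches 0.02 g/dL in at most 33 of 120, so the one-beer verdict does not change.

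**5. H1b1.** AUC(t) is the integral of TAC from session start. TAC is not negative, so AUC cannot fall. Median ratios at 30 : 60 : 90 minutes:

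- Proportional device, AUC: 1 : 4.2 : 9.7 at lag 0 (steps 3.2, then 5.5) and 1 : 7.1 : 21.0 at lag 30 (steps 6.1, then 13.9). A linear increase needs equal steps.
- Monitor that registers beer 1 only, lag 30, AUC: 1 : 5.3 : 10.2.
- Running peak at lag 30: 1 : 3.2 : 6.0 for the proportional device, 1 : 1.7 : 1.7 for the beer-1-only monitor.

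In the second model, one beer and nothing more gives an AUC of 0.056, 0.290 and 0.463 at its shortest lag, a rise of 0.463 / 0.056 = 8.3-fold.

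**6. H1b2, a separate sampling point.** 90 minutes / 30 = 3 BrAC readings for 3 beers. With about one reading per beer, the BrAC peak and time-to-peak for beers 1 and 2 are largely set by the schedule.

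**The case against.** The best defence is that the plan never says the fall must appear before the next beer. It says curves will be inspected, and cites sources that may hold the convention and were not available. That stands: what can be shown is that the window is not stated in this text. It does not rescue the rates, because neither window observes a one- or two-drink episode.

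Three stronger readings are tempting and are not supported.

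- *The reported threshold will be wrong, or will be three beers by design.* This holds only under a strict window that the plan does not state, or for certain lags and gains. Counting verdicts over the assumed grid would not settle it. Two settings sit exactly on 72 of 120 (two beers alone at lag 60, gain 1; one beer by 30 minutes at lag 0, gain 1.5), and using 12.5 g for 12.6 g changes which verdicts move.
- *Drinks and time are collinear, so nothing can be estimated.* They do coincide by schedule, but the plan fits no model containing both.
- *The lab says nothing about dose.* Running peak levels off when only beer 1 registers, so it keeps some dose information, mixed with delayed signal from earlier beers.

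It is also fair that H2a and H2b study varying numbers of drinks. They do so with self-reported dose, and they do not turn the lab readings into one- or two-drink rates.

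**Conclusion.** The point holds and should be fixed before analysis. That the beer 1 and beer 2 rates are cumulative readings at about 30 and 60 minutes follows from the schedule and needs no model. That a fall is rarely or never visible before the next beer rests on a material TAC delay, which the plan expects without sizing. The size of the error in the threshold is unknown. In the assumed model it falls mainly on the two-beer verdict, and the model counts are illustrations, not predicted rates. A rising cumulative AUC is not evidence of dose-response, and failure of linearity in it is not evidence against the device. Analyses of the full three-beer curve, and the two-session reliability analysis (H1c), are unaffected.

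**What to change.** Leave the drinking schedule as it is and change the Aim 1 analysis text and the wording of Hypothesis 1a.

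1. Make the full three-beer curve the main lab result for detection and for the TAC–BrAC comparisons.
2. Report beer 1 and beer 2 values as descriptive cumulative readings, with windows built from the recorded beer times and with stated AUC limits. Label the beer 1 detection rate a lower bound, and do not apply the 60% threshold to beers 1 and 2.
3. Do not read increasing cumulative AUC as dose-response. Present running peak by beer as descriptive and subject to delay.
4. Take any one- or two-drink detection rate from the field episodes that H2a already tabulates, with episode counts and person-clustered intervals.
5. State that per-beer BrAC peak and time-to-peak rest on about one reading per beer.

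This needs no new data or visits. The cost is that the lab part no longer claims a one-drink threshold, and the field estimate rests on self-report and possibly few one-drink episodes. The entry minimum of 5 drinking days in 30 implies 5 × 14/30 = 2.3 days per person in the field test, or about 93 over 40 people, of any size. If 60% were detected, the Wilson 95% interval would be 31–83% with 10 one-drink episodes, 42–75% with 30 and 46–72% with 50 (episode counts assumed), before any widening for clustering.

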Analysis plan for Aim 2. *Validate Skyn monitor in daily life using a 2-week ecological momentary assessment (EMA), and evaluate its acceptability and usability for daily use.* H2a. Agreement between monitor and self-reports in EMA. Using the same definition of a successful detection and procedure of determining drinking episode in monitor data as in

H1a, we will calculate the detection rates by self-reported number of drinks. A receiver operating characteristic (ROC) curve will be plotted. H2b: Relationship between TAC and number of drinks. First, simple correlations will be calculated to examine the association between TAC (peak, AUC) and self-reported number of drinks using all drinking episodes. Second, a multilevel analysis will be used to examine the association between TAC (peak, and AUC) and number of drinks accounting for nested data within person. Acceptability and Usability. Ratings of the Skyn monitor will be summarized on aspects such as wearability, ease to operate, satisfaction with the product, and willingness to wear.

Analysis plan for Exploratory Aim. *Explore factors that may be associated with individual differences in monitor readings.* T-tests or Chi-square will be used to examine group differences (e.g., male vs. female, HIV+ vs. HIV-) in TAC parameters (i.e., peak, time-to-peak) and their relationships with # of drinks and BrAC.

Sample size and power. This is for how many participants need to complete the study. For Aim 1, the sample size was based on prior laboratory validation studies of transdermal alcohol monitors.^{36,45,57} Also, power analysis shows that a sample size of 40 will give us 80% power to detect a correlation $\geq .60$. For Aim 2, power analysis shows that $n = 40$ will give us 90% power ($\alpha = .05$) to detect an effect size $\geq .13$ in a multilevel analysis with $r = .60$ between measures.^{58,59} For Exploratory Aim, $n = 20$ in each group can give us 80% power to detect a large difference ($d \geq .80$).

7. Possible Discomforts and Risks:

Potential risks in this study include:

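### Detection in H1a and H2a is a visual call without fixed numeric criteria, made with no stated masking to when alcohol was drunk

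*Combined protocol and SAP*

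**What the plan says.** The Aim 1 analysis plan sets a pass mark for H1a: "We define the threshold of detection as the consumption level with a 60% or higher detection rate". It applies this at three levels: "Rate of successful detection at the end of 1 beer, 2 beers, and 3 beers will be calculated respectively". The method is visual: "This will be done by observing the data series and curves from the monitor readings". A detection needs three features:

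- a TAC peak, with 0.02 g/dL offered as an example only;
- a rise, "with a reasonably visible elevation slope for absorption";
- a fall, described as "a declination slope for elimination (i.e., TAC curve goes down at the reasonable pace").

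No baseline, slope, duration or time window is given. The Aim 2 plan carries this into H2a: "Using the same definition of a successful detection and procedure of determining drinking episode in monitor data". It then tabulates detection rates by self-reported number of drinks and plans an ROC curve.

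Other parts of the Research Plan bear on what a reader can know:

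- **Lab Session 1:** every participant drinks three beers, each within 15 minutes and followed by a 15-minute break.
- **Data sources and management:** start and end times of each beer are recorded, and all data are linked by participant ID.
- **EMA:** researchers can see uploaded drinking reports in real time.

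The documents do not say who reads the curves, what that person has in view, or whether a second reading is made.

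**The concern.** In a validation study the reading of the device under test should be made without knowledge of the reference, by a rule that another user could repeat. Neither is secured here.

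Every H1a call is made on a session in which alcohol is known to have been given. H1a scores only the levels after one, two and three beers, so a lenient reader pays no false-positive penalty in the lab. In H2a a reader who knows the EMA times could raise apparent agreement in both directions, by passing curves at reported times and rejecting them elsewhere.

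At stake are the H1a conclusion on the lowest detectable consumption level, which Hypothesis 1a illustrates with one drink, and the H2a detection rates. The H2a ROC curve is also affected, because a yes/no visual call gives no defined score whose cut-off can be varied.

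**Working it through.** The plan gives no sample size, power or precision for a detection rate, so there is no stated figure to reproduce. The Aim 1 power statement concerns a correlation. What can be checked is how sensitive the 60% mark is to a few discretionary calls.

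**Inputs from the documents.** The mark is 60% (H1a). There are 40 planned completers (Overview; Sample size and power).

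**Assumed inputs, not in the documents.** p is the true detection rate at a given level. f is the share of truly undetected curves that a lenient reader passes.

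**Step 1: calls needed to reach the mark.** 60% of 40 is 24. From a true 50%, 24 − 20 = 4 calls; from 55%, 24 − 22 = 2; from 40%, 24 − 16 = 8. Four calls at a true 50% means that 4/20 = 20% of the misses are passed.

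**Step 2: chance of meeting the mark.** The observed rate is q = p + (1 − p)f. The chance is P(X ≥ 24) with X ~ Binomial(40, q), computed exactly.

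| True p | f = 0 | f = 10% | f = 20% |
|---|---|---|---|
| 0.40 | q = 0.40: 0.8% | q = 0.46: 5.3% | q = 0.52: 19.7% |
| 0.50 | q = 0.50: 13.4% | q = 0.55: 31.9% | q = 0.60: 56.8% |
| 0.55 | q = 0.55: 31.9% | q = 0.595: 54.2% | q = 0.64: 75.8% |

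**Step 3: precision at the mark.** The exact 95% interval for 24/40 is 43.3% to 75.1%, so a rate at the mark is imprecise even with perfect reading.

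**Step 4: other denominators.** The Overview lets some participants do the field test only, so lab completers could be fewer than 40. If there were 20 (an assumption), 12/20 is needed and two calls lift 10/20 to the mark. At a true 50% the chances become 25.2%, 41.4% and 59.6%. If both lab sessions were counted for 40 people, the denominator would be 80 and eight calls would be needed (40/80 to 48/80).

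**Step 5: the opposite direction.** A detection needs a fall, but the next beer starts 15 minutes after the last one ends. A decline after beer 1 or 2 may never show, and a strict reader would score those levels as missed whatever the monitor did. At the mark, one strict call is enough: 23/40 = 57.5%.

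**The case against.** The strongest reply is that the plan is silent on masking, which differs from saying that the reader is unmasked. TAC files are downloaded separately and later, and linkage by ID for analysis does not show that the curve reader had the drinking times. That stands for the exact times. It does not remove the fact that every lab session is known to contain three beers on a fixed schedule.

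A reader might infer that the rates will be inflated. The documents do not support that. The criteria are partly anchored, since a peak, a rise and a fall are all required, and Step 5 shows a route to rates that are too low. The size of any reader effect cannot be derived either: the 50% true rate is chosen for illustration, and at a true 40% even f = 20% meets the mark only 19.7% of the time.

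A reader might also infer that all of Aims 1 and 2 rests on this call. It does not. H1b, H1c and H2b use peak, area under the curve or time-to-peak. H1a itself is descriptive, in a project the protocol calls exploratory.

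Finally, the plan cites sources for its visual procedure. The reference list supplied stops before them, so whether they contain a numeric rule cannot be checked. The protocol text does not state one.

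**Conclusion.** The concern holds as a weakness in how the outcome is defined and read. The detection call is subjective by design, has no fixed numeric criteria, and is not protected from knowledge of the reference. As written, another user of the monitor could not reproduce the H1a rates or the H2a detection rates. The direction of any bias is open.

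The size is illustrative only: four calls in 40 separate a true 50% from the 60% mark, and passing 10% or 20% of undetected curves moves the chance of meeting it from 13.4% to 31.9% or 56.8%. These figures assume the true rate, the reader's leniency, 40 lab completers and one curve per participant per level. The number of lab completers and the share of equivocal curves are not known from the documents. The change should be made before curves are read.

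**What to change.** Before any curve is inspected, fix numeric criteria: peak, minimum rise above baseline, minimum duration of rise, and fall from the final peak. Then:

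1. Apply them by script to each lab session and to the whole field record, without beer times or EMA entries as input.
2. Only afterwards match detections to beer or EMA times, using a window set in advance. The window should allow for the delay from BrAC to TAC peak that H1b2 expects.
3. For the 1- and 2-beer levels score the rise only; require the fall only after the last beer.
4. Take the lab baseline from pre-drinking readings where the temperature sensor shows the monitor was worn. Wear before the first beer is not assured, because the instruction to wear the monitor appears at the start of drinking, so state how sessions without such readings are handled. Set the field baseline by a rule that does not use EMA.
5. Report the false-positive rate on field days with no reported drinking, noting that unreported drinking would count as false positives.
6. Build the H2a ROC curve from a numeric score such as peak rise.

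If visual reading is kept, make it secondary. The existing reader should work from files stripped of times, in random order, mixed with alcohol-free segments.

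The cost is protocol wording and a short script, with no added visits or staff. A fixed rule may miss some atypical curves that a reader would accept, so rates may be somewhat less favourable.

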For those who are deemed eligible for the study after the in-person screen, they will also complete the baseline survey (can be sent via email), where they will answer questions on demographics, drinking history, alcohol use disorder, alcohol effects, drinking motives, other substance use, and HIV treatment/adherence (for HIV+ participants only). Information obtained from these questions will be used to explore factors contributing to interpersonal variations in transdermal alcohol concentration and how they impact participant compliance in the field test (as some preliminary findings for building a larger project on this exploratory R21).

Lab Session 1. Participants will be asked not to eat for 3 hours pre-arrival, and arrive with a non-positive BrAC reading (.00%) detected by a laboratory degree breathalyzer (Alco-Sensor VXL, Intoximeters). In the event that an individual registers a positive breath alcohol level, there will be two possibilities. If the individual's breath alcohol level is likely to decline to 0.00% in a reasonable amount of time (i.e., 0.02% or lower), they will be offered the chance to remain at the research facility to be re-tested and take part in the appointment when their breath alcohol level reaches 0.00%. If it is not feasible for the participant to wait, they will be offered one opportunity to reschedule this appointment. Instruction/practice of the EMA app, Skyn monitor and its app will take place prior to the drinking session when participants are sober. The RA will help participants download the EMA app (Sec.4.4) on their smartphone, enter an 8-digit unique ID code for each participant, and show them how to enter a drinking session and answer the prompted questions. The RA will also help download the Skyn app and show participants how to pair the app with the monitor. The recording of data should automatically begin once the Skyn monitor is paired with the app. Instructions and demonstration of how to charge and operate the Skyn monitor will also be given. Procedures for the two-week field test will be explained. Participants will have time to

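### H1b2 reads a zero slope of the TAC-BrAC difference on the TAC-BrAC average as absence of bias across BrAC levels, but that slope is zero exactly when the two SDs are equal, so it cannot support the conclusion.

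*Combined protocol and SAP*

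**What the plan says.** The text is in the combined protocol and SAP, section 6 (Research Plan), Analysis plan for Aim 1, H1b2. Peak TAC and peak BrAC are to be compared in three ways: a correlation with a scatter plot, a Bland-Altman plot, and the delay between the two peaks.

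For the Bland-Altman plot the axes are fixed: "The average of paired TAC and BrAC peak values are plotted on x-axis, and the difference between them on y-axis". The interpretation follows: "Stable TAC results across all BrAC levels will line up with a zero slope, which will suggest there is no systematic bias in estimating BrAC". The plot is repeated by dose: "All these analyses will be conducted for TAC and BrAC readings obtained after each beer respectively".

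No test, significance level, confidence interval or tolerance is given for the slope. The plan does not say what a non-zero slope would mean.

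**The concern.** The sentence makes a claim about each BrAC level: that the expected TAC-BrAC difference does not change as BrAC changes. The horizontal axis, however, is the average of the two readings, and TAC's own random error enters both that average and the difference. The slope therefore mixes two things: how TAC responds to BrAC, and how noisy TAC is.

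The stake is what H1b2 may conclude about validity against the breathalyzer. A monitor that under-responds to BrAC could be reported as free of level-dependent bias because its noise makes up the lost spread. If the rule is also read in reverse, plain measurement noise could be reported as level-dependent bias.

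**Working it through.** **Inputs**
- Axes and reading rule: H1b2.
- Pairs per plot: 40, from Sample size and power. I add n = 20 as an assumption, because the Overview lets some people skip the lab part ("Participants will be invited to complete all components of the study or only the field test portion given the COVID pandemic").
- TAC-BrAC correlation r: not given. I use .60 to .90.
- SDs and error variances: not given. I set SD(BrAC) = 1.
- Slope test: none stated. I assume two-sided .05; the plan gives an alpha only for Aim 2.
- Simulations: 20,000 normal samples per case, with simulation error of about half a percentage point.

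**The plan's own figure.** There is none for the slope. The only Aim 1 figure is that "power analysis shows that a sample size of 40 will give us 80% power to detect a correlation" of .60 or more. By Fisher's z, √37 × atanh(.60) − 1.96 = 2.256, which is 98.8% power; n = 20 gives 81.5%. That mismatch is a separate matter and does not enter below.

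**Step 1: what the slope measures.** With T = TAC peak and B = BrAC peak,

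Cov(T − B, (T + B)/2) = (Var T − Var B)/2.

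This needs no distributional assumption. The slope is zero if and only if SD(T) = SD(B).

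**Step 2: a compressed monitor.** Let T = constant + b·B + error, with correlation r. Then Var T = b²/r². With b = r = .60, Var T = 1 and the expected slope on the average is 0, although TAC rises only .6 per unit BrAC. At n = 40 the slope on the average is flagged 5% of the time. Regressing T − B on B has expected slope .60 − 1 = −.40 and is flagged 84% of the time.

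**Step 3: an unbiased, noisier monitor.** Set b = 1, so E[T|B] = B and Var T = 1/r². The expected slope on the average is 2(1/r² − 1)/(1/r² + 3). For r = .60: 2 × 1.778/5.778 = .615.

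| r | SD ratio 1/r | Expected slope | Flagged, n = 40 | Flagged, n = 20 |
|---|---|---|---|---|
| .60 | 1.67 | .62 | 97% | 76% |
| .70 | 1.43 | .41 | 86% | 55% |
| .80 | 1.25 | .25 | 62% | 34% |
| .90 | 1.11 | .11 | 31% | 17% |

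The share passes one half below about r = .83 at n = 40 and below about r = .72 at n = 20. At r = .83 the TAC error SD is √(1/.83² − 1) = .67 of the between-person SD of BrAC peaks. Regression on error-free BrAC flags the same monitor about 5% of the time throughout.

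**Step 4: error in the BrAC peak.** If BrAC peaks have reliability λ, ordinary regression of the difference on BrAC for an unbiased monitor has expected slope λ − 1. Share flagged at n = 40, where r is now the correlation of TAC with true BrAC (.60 / .70 / .80 / .90):

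| λ | Slope on BrAC | On the average | On BrAC |
|---|---|---|---|
| .95 | −.05 | 95 / 79 / 48 / 17% | 6 / 6 / 7 / 9% |
| .90 | −.10 | 92 / 70 / 36 / 10% | 7 / 9 / 12 / 20% |
| .80 | −.20 | 82 / 48 / 17 / 5% | 17 / 24 / 34 / 54% |

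BrAC error lowers the false flags on the average axis and raises them on the BrAC axis.

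**The case against.** Difference against average is the standard Bland-Altman display, and its slope is a fair check when the two devices have equal error variances: simulated with r = .60, an unbiased pair is then flagged 5% of the time. This stands. It is a reason to keep the plot. The plan does not claim equal precision, and it sets a wrist-worn monitor under validation against a laboratory-grade breathalyzer.

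A reader might go further and infer that a monitor that is unbiased but noisy will usually be declared biased. The documents do not support that:
- The plan states only the zero-slope direction, in cautious terms and without a test. The reverse rule and the 5% test are assumptions of this review.
- The .60 in Sample size and power is a minimum detectable correlation for Aim 1, not an expected TAC-BrAC value, so the 97% is one end of a range.
- Most trials are affected only below the r limits in Step 3, and fewer if BrAC peaks carry error.

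The breathalyzer peak may indeed carry error. Under Lab Session 1, BrAC is read every 30 minutes while drinking and each beer takes a 30-minute slot, so a per-beer peak during drinking may rest on about one reading. Ordinary regression on BrAC is therefore not safe as the sole replacement.

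Finally, the stakes are limited. Hypothesis 1b concerns correlation, the planned scatter plot would partly reveal a compressed response, and no decision is tied to the slope.

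**Conclusion.** The inference in H1b2 is wrong as written. A zero slope on the average shows equal SDs, not absence of bias across BrAC levels, and this follows from an identity.

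The failure that the sentence itself permits is a compressed response passing as unbiased: 5% flagged, against 84% on the BrAC axis, for a response of .6. That example assumes r = .60, equal SDs, error-free BrAC, n = 40 and a two-sided 5% test.

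The opposite failure is conditional. It needs a non-zero slope to be read as bias, and its frequency runs from 97% to 31% as r goes from .60 to .90 at n = 40 with error-free BrAC. It should not be presented as the usual outcome of this trial, because the documents give neither the TAC-BrAC correlation nor the error of either device.

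**What to change.** - Keep the Bland-Altman plot, the mean difference and the limits of agreement as description.
- Delete the statement that a zero slope on the average suggests no systematic bias.
- Judge level-dependent bias by the slope of TAC peak on BrAC peak against 1 (equivalently, the difference on BrAC against 0), with a 95% CI. Take it from an errors-in-variables (Deming) fit over a stated range of BrAC-peak reliability, e.g. .80 to 1.0, with ordinary regression as the 1.0 end.
- Draw a conclusion about bias only if it holds across that range. For a given reliability the corrected slope is the ordinary slope divided by it. An ordinary slope of .60 becomes .60/.80 = .75 at the lower end, so the CI would have to exclude 1 at both ends before compression is concluded.

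The cost is a few sentences in the analysis plan and one further fit to the same pairs, with no new data. The downside is that the conclusion depends on an assumed BrAC reliability and the interval is wider: treating the reliability as known, by a factor of 1/.80 = 1.25 at the lower end.
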